## SUMMARY

**Background:** Animal studies strongly suggest that cooling improves outcome after ischaemic stroke. Cooling is probably most efficacious with temperatures of 34°C or below, but such temperatures may not be tolerated well by awake patients on a stroke unit. Cooling to 35°C may have a smaller but still substantial effect on outcome and may be achievable for large numbers of patients with ischaemic stroke. Large randomised clinical trials testing whether cooling improves outcome in patients with acute ischaemic stroke are warranted, but the optimal strategies to achieve hypothermia are uncertain. The aim of this pilot phase is to compare the feasibility and safety of surface cooling to 35°C, started within 4.5 hours after the onset of acute ischaemic stroke and maintained for 12 hours, with strategies aimed at reaching a temperature of 33°C and/or maintaining hypothermia for 24 hours.

**Methods:** This is a pilot phase for a randomised, open, multi-centre, phase III international clinical trial with masked outcome assessment, comparing four different surface cooling strategies with standard treatment in awake adult patients with acute ischaemic stroke. A total of 24 patients will be randomised in the Edinburgh pilot, with a further 2-3 pilots planned elsewhere in Europe. Patients will be randomised to conventional treatment (8 patients) or to one of the following four surface cooling strategies (4 patients each): (A) 35°C maintained for 12 hours; (B) 33°C maintained for 12 hours; (C) 35°C maintained for 24 hours or (D) 33°C maintained for 24 hours. Before randomisation begins we will recruit 3 patients to be cooled to 35°C maintained for 12 hours (but without the biomarker component) to streamline the patient pathway. In the randomised pilot phase we will use a dose escalation approach to ensure that the longer cooling duration is only performed once we have gained sufficient experience with shorter duration cooling.

In all patients randomised to hypothermia, cooling will be started within 4.5 hours of the onset of symptoms by means of intravenous infusion of 20 ml/kg cooled normal saline (4°C) over 30 minutes, followed by surface cooling using the Arctic Sun device. Shivering and discomfort will be prevented and if necessary treated with intravenous pethidine. The primary objective is to determine the feasibility, tolerability and safety of the various cooling strategies, as evidenced by the primary endpoint, the proportion of completed interventions. Secondary outcome measures include measures of the safety and tolerability of the intervention.

## 1. INTRODUCTION

### 1.1 BACKGROUND

Acute ischaemic stroke is a condition caused by occlusion of one of the cerebral arteries or arterioles and is typically characterised by the sudden onset of a focal neurological deficit. Common deficits include dysphasia, dysarthria, hemianopia, weakness, ataxia, and sensory loss. In Western communities, about 80% of strokes are ischaemic; the other strokes are haemorrhagic.

The social and economic burden of stroke is enormous. Stroke is the second cause of lost disability-adjusted life years in high-income countries and the second cause of death world wide. In people aged 55 years or more, the incidence generally ranges from 4.2 to 6.5 per 1,000 person years. The direct lifetime costs per ischaemic stroke in Germany have recently been estimated at € 43,129. Rehabilitation and chronic nursing care account for the largest part of these costs. As stroke incidence rates rise exponentially with age, the social and economic burden of stroke will rise further with the ageing of the population.

#### 1.1.1 The Ischaemic Penumbra

Ischemic brain injury results from a cascade of events running from energy depletion to necrosis or apoptosis. Intermediate factors include excitotoxicity, free radical formation, and inflammation. Initially after arterial occlusion, a central core of very low perfusion is surrounded by an area with dysfunction from metabolic and ionic disturbances, but in which structural integrity is still preserved, the so-called ischemic penumbra. In the first minutes to hours, clinical deficits therefore do not necessarily reflect irreversible damage. For this reason, the penumbra is the target of treatment for acute ischaemic stroke. Depending on residual blood flow and duration of ischemia, the penumbra will eventually be incorporated in the infarct if reperfusion is not achieved.

#### 1.1.2 Current Treatment Options

Based on the concept of a salvageable ischaemic penumbra, about 500 'neuroprotective' treatment strategies have shown to improve outcome in animal models of acute ischaemic stroke. By contrast, only very early intravenous thrombolysis with recombinant tissue plasminogen activator (rt-PA) and aspirin are incontrovertibly efficacious in patients, despite innumerable clinical trials of other treatment strategies in acute ischaemic stroke. Intravenous thrombolysis is currently restricted to a three-hour time window, and even in high-income countries, only a very small minority (generally 3-7%) of patients with acute stroke receive this therapy. Aspirin can be given to a broad range of patients with acute ischaemic stroke, but the benefit is small, with a NNT of 77 to prevent poor outcome in a single patient. For this reason, there is an obvious need for additional and more effective treatment strategies that are broadly applicable.

In summary, animal studies strongly suggest that cooling improves outcome after ischaemic stroke. Cooling is probably most efficacious with temperatures of 34°C or below, but such temperatures may not be tolerated well by awake patients on a stroke unit. Cooling to 35°C may have a smaller but still substantial effect on outcome and may be achievable for large numbers of patients with ischaemic stroke. Large randomised clinical trials testing whether cooling indeed improves outcome in patients with acute ischaemic stroke are therefore warranted. To inform such trials, the current pilot phase will test and compare the feasibility, tolerability and safety of different depths and durations of hypothermia in awake patients with acute ischaemic stroke.

## 1.2 RATIONALE FOR TRIAL

### 1.2.1 Rationale for Hypothermia

One of the reasons for the failure of allegedly neuroprotective compounds in patients may be that most inhibit only a single step in the chain of events leading to cell death. By

contrast, hypothermia affects a wide range of cell death mechanisms, including energy depletion, disruption of the blood-brain barrier, free radical formation, excitotoxicity, and inflammation. The potential of hypothermia is underlined by randomised clinical trials in patients with global cerebral ischemia after cardiac arrest and in infants with moderate or severe hypoxic-ischemic encephalopathy. In addition, several prospective observational studies have shown an association between a raised body temperature and poor outcome after stroke on the one hand, and low body temperature and improved outcome on the other. Next to reperfusion strategies, hypothermia therefore is the most promising therapeutic modality for patients with acute ischemic stroke.

### 1.2.2 Previous and Ongoing Studies

So far, clinical trials of cooling in patients with acute ischemic stroke have been too few and too small to allow any conclusions. The Cooling for Acute Ischemic Brain Damage (COOL AID) trial is the only published randomised controlled trial and included just 40 patients where cooling to a target temperature of 33°C for 24 hours was initiated within 12 hours of stroke onset using intravascular cooling. The Nordic Cooling Stroke Trial (NOCSS) was a randomised trial which tested the effect of surface cooling to 35°C initiated within 6 hours of stroke. Unfortunately, the trial was recently terminated because of slow recruitment after the inclusion of 44 patients against a target recruitment of 1,000 ([name], personal communication). The ongoing Intravascular Cooling for the Treatment of Stroke – Longer window (ICTuS-L) trial is a phase II trial designed to investigate the feasibility and safety of a combination of intravenous thrombolysis and intravascular cooling to 33°C. The only large temperature-driven phase III randomised acute stroke trial is the Paracetamol (Acetaminophen) In Stroke (PAIS) trial, which sought normalisation of temperature rather than hypothermia; overall, this showed no benefit, although in a post hoc analysis there was a suggestion that patients with pyrexia at entry may have benefited.

### 1.2.3 Depth of Hypothermia

COOL AID, as well as most randomised trials of hypothermia in postanoxic encephalopathy after cardiac arrest, perinatal hypoxic-ischemic encephalopathy, and traumatic brain injury have tested cooling to levels of 32°C to 34°C. For patient comfort, monitoring, and the prevention of shivering, hypothermia to these levels generally requires sedation, mechanical ventilation, and therefore admission to an intensive care unit. Due to the limited availability of intensive care beds in most countries, treatment of even a minority of acute stroke patients is therefore precluded by substantial practical and logistical problems. The fact that intensive care treatment has long been common clinical practice for patients with severe traumatic brain injury or after cardiac arrest may explain why large and definitive randomised clinical trials of moderate hypothermia have been accomplished in these patient populations, whereas such trials have not even been started in patients with acute ischaemic stroke.

In a recent systematic review and meta-analysis of hypothermia in animal models of acute ischaemic stroke, hypothermia reduced infarct size by more than 40% with temperatures of 34°C or below. However, infarct size was still reduced by 30% (95% confidence interval (CI), 21 to 39%) with cooling to 35°C, suggesting that even very modest cooling has considerable potential as a neuroprotective strategy. Temperature reductions to 35.5°C or 35°C have been shown feasible and safe in awake patients with acute ischaemic stroke by surface cooling, in combination with pethidine (meperidine) to treat shivering. With a similar strategy, body temperature could be reduced to 34.5°C in awake patients with acute myocardial infarction.

### 1.2.4 Time to Start of Treatment

Based on preclinical studies, time is the most critical factor in the treatment of stroke. A pooled analysis of six randomised trials of intravenous thrombolysis with rt-PA has suggested a potential benefit up to six hours after stroke onset, but the benefit was greater the sooner treatment was started. Expediting the delivery of care should therefore be a crucial factor in any acute stroke trial.

In the above-mentioned meta-analysis of animal studies, the effect of hypothermia was most consistent when treatment was started before or at the onset of ischaemia, but the benefit remained substantial with treatment delays of up to six hours. In the European Hypothermia After Cardiac Arrest Trial, cooling improved functional outcome despite a median interval of eight hours between the restoration of spontaneous circulation and the attainment of the target temperature. There are no data on the maximum time to start of cooling in patients with acute ischaemic stroke. However, it is expected that a potential benefit will be greater the earlier cooling is started.

#### 1.2.5 Reperfusion

On the first day after stroke onset, spontaneous reperfusion occurs in only a minority of the patients. Even after intravenous thrombolysis, complete recanalization of an occluded middle cerebral artery (MCA) two hours after start of treatment is found only in up to one third of patients. In the first hours after stroke onset, most infarcts will therefore still lack adequate perfusion. In animal models of focal cerebral ischaemia, efficacy was higher in temporary rather than permanent MCA occlusion, but the reduction in the latter was still substantial (37%; 95% CI, 30 to 43%). This suggests that hypothermia may be efficacious irrespective of the occurrence of reperfusion.

#### 1.2.6 Thrombolysis

Together with aspirin, intravenous thrombolysis with rt-PA is the only pharmacological treatment of acute ischaemic stroke of proven benefit. With the exclusion of a small subgroup of patients in the COOLAID-studies, there is no substantial patient data on the combination of hypothermia and thrombolysis. In vitro studies have shown that the fibrinolytic activity of rt-PA is reduced at lower temperatures. However, the effect appears to be small: for each degree decrease in temperature the amount of in vitro clot lysis decreased by about 0.5%. Data from animal models are limited. In older studies, hypothermia appeared to have no effect on vessel opening, and to augment the protective effect of rt-PA. However, these results may be confounded by an increase in mortality in animals receiving both rt-PA and hypothermia. Recent experimental data indicate that in comparison to thrombolysis alone, a combination of cooling to 34°C and thrombolysis by rt-PA reduces both infarct size and parameters associated with the disruption of the blood brain barrier. Combination therapy did not change perfusion parameters as measured by perfusion weighted imaging (PWI).

#### 1.2.7 Duration of Hypothermia

Adequate information on the optimal duration of hypothermia in patients with ischaemic stroke is lacking. In the above-mentioned systematic review of hypothermia in animal studies of focal cerebral ischaemia, cooling for more than six hours was slightly less efficacious than cooling for two hours or less. However, as the analyses were not adjusted for potential confounders, this finding should be interpreted with caution. In animal models of focal cerebral ischaemia, the diverse pathophysiological processes which are invoked exert their deleterious effects over different timecourses extending from the first hours to several days after vessel occlusion. Such observations would suggest that hypothermia should be more efficacious if prolonged. In clinical trials of cardiac arrest, hypothermia has been proven efficacious if maintained for 12 or 24 hours.

#### 1.2.8 Modes of Hypothermia

Two major methods of inducing hypothermia in stroke patients can be distinguished: surface cooling and endovascular cooling. Surface cooling methods include convective air blankets, water mattresses, alcohol bathing, and ice packing. These methods have the advantage of being non-invasive, cheaper than endovascular cooling, and are probably applicable on a larger scale as experience with introducing catheters in large veins is not required. Disadvantages include a slower rate of temperature reduction, a more difficult control at the target temperature, and patient discomfort. Endovascular cooling is generally faster and patient comfort may be greater if warming blankets are applied. Disadvantages are its invasive nature, its preventing hypothermia concurrent with thrombolysis, and the

required experience with endovascular techniques, thus preventing an easy wide-spread application.

Surface cooling has been shown feasible and appears appropriate for temperature reductions in awake patients to about 35°C if intravenous pethidine is administered to prevent shivering and for patient comfort;  in animal studies pethidine has no impact on the neuroprotective effects of hypothermia. For a more rapid induction of hypothermia, chilled intravenous fluids may be infused at the onset of surface cooling.

### 1.2.9 Temperature Measurements

Common temperature measurements include those in the rectum, bladder, tympanum, oesophagus, or arteries. It is not known which of these reflect temperature in ischaemic brain tissue best. In trials of hypothermia in cardiac arrest, target temperatures were measured in the bladder or in the pulmonary artery.

## 2. TRIAL OBJECTIVES

### 2.1 OBJECTIVES

#### 2.1.1 Primary Objective

To compare the feasibility, tolerability and safety of surface cooling to 35°C, started within 4.5 hours after the onset of acute ischaemic stroke and maintained for 12 hours with similar strategies aimed at reaching a temperature of 33°C and/or maintaining hypothermia for 24 hours.

#### 2.1.2 Secondary Objectives

To identify which peripheral temperature measurement (oesophageal, tympanic) best reflects temperature in ischaemic brain tissue; to determine the feasibility of collecting serum and DNA samples in a larger trial; and to identify which panel of biomarkers might best be taken forward to that trial.

### 2.2 ENDPOINTS

#### 2.2.1 Primary Endpoint

- Proportion of patients completing the intervention per protocol.

#### 2.2.2 Secondary Endpoints

- Feasibility (recruitment rate; time to target temperature; stability at target; control of temperature during warming period)
- Tolerability (Columbia Shivering Score; patient questionnaire)
- Safety (deaths; adverse events including infections, DVT or coagulopathy; pethidine dose required)
- Oesophageal temperatures compared with tympanic, and bladder and/or rectal where available, at baseline, every 15 minutes in the first three hours after start of cooling and every 30 minutes thereafter until 48 hours after stroke onset
- Penumbra temperature 3 hours after initiation of cooling
- National Institutes of Health Stroke Scale (NIHSS) score, the Barthel Index (BI) and the modified Rankin scale (mRS) at three months
- Infarct volume on CT or MRI 7 days after the induction of hypothermia
- Temperature in ischaemic core, surrounding brain, and contralateral hemisphere determined using MR spectroscopy initiated 2-3 hours after the commencement of cooling
- Feasibility of collecting and processing samples for future biomarker study.

### 3. TRIAL DESIGN

This is a randomised, open, multi-centre, pilot phase trial for a phase III international clinical trial with masked outcome assessment, comparing the combination of cooling and best medical treatment with best medical treatment alone in patients with acute ischaemic stroke. 24 patients will be recruited in Edinburgh. Other European centres plan to conduct similar pilot studies (involving around 100 patients over 4 centres) and we will align our study protocols to allow pre-planned meta-analysis of feasibility, safety, tolerability and efficacy data. The trial will be approved by appropriate review boards in each participating centre. The University of Edinburgh will act as trial sponsor within the EU.

Outcome measures to assess feasibility, tolerability, and safety include the following:

#### Feasibility

- Compliance: the proportion of completed interventions (completed = a treatment that is continued until the end of the predefined time period, or earlier in cases where the patient has fully recovered)
- Time to first reaching target oesophageal temperature
- Stability at target temperature (time spent with oesophageal temperature within 0.7°C of target)
- Control of warming (per-protocol rewarming to 36°C taking at least 3 hours 20 minutes (35°C group) or 10 hours (33°C group)).

#### Tolerability

- Columbia Shivering Score (measured every 15 minutes during the cooling and rewarming period)
- Patient questionnaire and interview with trial nurse (performed at 7 days or hospital discharge).

#### Safety

- Neurological deterioration, defined as an increase of more than 4 points on the NIHSS at day 7 after the induction of hypothermia
- Hypotension, defined as a mean arterial pressure of less than 70mmHg sustained for 10 minutes or more
- Haemorrhagic complications, i.e. symptomatic intracranial haemorrhage or any other haemorrhage requiring blood transfusion
- Infections, i.e. pneumonia, urinary tract infection, and other infections, defined according to the modified Centre for Diseases Control criteria
- Reduction in level of consciousness requiring Intensive Care Unit admission
- Any skin injury or reaction at the cooling site
- Gastrointestinal haemorrhage.

In this trial the primary temperature measurement is oesophageal. This will be monitored continuously and compared with tympanic temperature measurement every 15 minutes during cooling and hourly thereafter until 48 hours after stroke onset; and with penumbra temperature (using MR spectroscopy) at 3 hours after the start of cooling.

Other outcome measures will include the scores on the NIHSS, the Barthel Index (BI) and the modified Rankin scale at three months, and infarct volume on CT or MRI at day 7.

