#### **5.6.2 Treatment Allocation**

All patients will be managed in the High Dependency Unit at the Western General Hospital. Because of the potential discomfort of prolonged cooling to low temperatures, and the learning required efficiently to deliver cooling to awake patients, we will randomise in blocks of 12, each block including 4 patients allocated to standard care. The first 12 patients will be randomised 1:1:1 to 35°C for 12 hours; 33°C for 12 hours; or standard care (Groups A and B). Patients 13-24 will be randomised 1:1:1 to 35°C for 24 hours; 33°C for 24 hours; or standard care (Groups C and D).

In all patients randomised to hypothermia, cooling will be started within 4.5 hours after the onset of symptoms and within 90 minutes of hospital admission by means of intravenous infusion of 25ml/kg refrigerated normal saline (4°C) over 30 minutes.

In patients randomised to hypothermia, surface cooling will be applied to the thighs and chest immediately after the start of the saline infusion using five Arctic Sun Energy Transfer Pads, connected to an Arctic Sun temperature control module with integrated chiller (Medivance, Inc). Inlet water temperature will be automatically controlled to achieve a target oesophageal temperature of 35°C or 33°C.

Start of treatment will be defined as the start of cooling, i.e. start of infusion of refrigerated saline. Active cooling will be continued for 12 or 24 hours. Thereafter, patients will be passively warmed at a rate controlled by the cooling device to be at most 0.3°C per hour until the oesophageal temperature is 36°C; the cooling device will then be disconnected.

Oesophageal temperature will be measured with probes providing feedback to the Arctic Sun. In addition to the continuous oesophageal recordings, tympanic temperature will be recorded before cooling is started and subsequently at 15-minute intervals with a standard tympanic thermometer. Where other temperature measurements are made as part of standard care, these data will also be recorded. Level of consciousness, presence or absence of shivering, blood pressure and heart rate will be recorded every 15 min for the whole cooling and warming phase.

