### **6.0.3 Randomisation Through to Day 7 ( $\pm$ 1 day; or discharge, if earlier)**

1. Date and time of randomisation
2. Date and time of start of cooling
3. Level of consciousness, presence of shivering, rectal, bladder, and tympanic temperatures, blood pressure, and heart rate every 15 minutes in the first three hours after start of cooling, every 30 minutes thereafter until 12 hours after start of warming, and every 6 hours until day 7 (or discharge, if earlier)
4. Laboratory tests, including full blood count, serum glucose, electrolytes, PTT, aPTT, C-reactive protein, blood samples for biomarker and genetic studies. 12-lead electrocardiogram 6 and 12 hours after randomisation, and at 48 hours
5. NIHSS at 24 and 48 hours and at 7 days (or discharge, if earlier)
6. mRS and BI at day 7 (or discharge, if earlier)
7. Concurrent medication
8. Neurological and systemic adverse events
9. CT or MRI scan at day 7  $\pm$  2 days

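### Protocol sections conflict on observation intervals, no stated interval can establish the 10-minute hypotension criterion, and controls have no defined early schedule

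*Protocol*

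**What the plan says.** **Hypotension.** Section 3 (Safety) gives the definition: "Hypotension, defined as a mean arterial pressure of less than 70mmHg sustained for 10 minutes or more". No repeat reading or continuous pressure recording is specified.

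**Blood pressure, consciousness and shivering.** Section 5.6.2 charts them on one interval: "presence or absence of shivering, blood pressure and heart rate will be recorded every 15 min for the whole cooling and warming phase". Section 6.0.3 lists the same items but charts them "every 15 minutes in the first three hours after start of cooling, every 30 minutes thereafter until 12 hours after start of warming", and 6-hourly after that to day 7 or discharge.

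**Shivering.** Section 3 (Tolerability) asks for a graded score: "Columbia Shivering Score (measured every 15 minutes during the cooling and rewarming period". Section 5.6.2 adjusts pethidine on a four-point scale. The charting lists in 5.6.2 and 6.0.3 name only whether shivering is present.

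**Tympanic temperature.** Section 2.2.2 has 15-minute readings for three hours, then "every 30 minutes thereafter until 48 hours after stroke onset". Section 3 has "every 15 minutes during cooling and hourly thereafter until 48 hours after stroke onset". Section 5.6.2 has 15-minute intervals with no stated end. Section 6.0.3 has the 15-minute, 30-minute and 6-hourly pattern above. Oesophageal temperature, the primary measurement, is recorded continuously under sections 3 and 5.6.2 but does not appear in the 6.0.3 list.

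**Controls.** Section 7.1 uses the 8 untreated patients for broad safety inferences. Section 5.6.2 places every patient in the High Dependency Unit.

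**The concern.** Site staff have two different instructions for the same vital signs, and an analysis plan cannot recover readings that were never taken. The hypotension definition needs information on a 10-minute scale, while the shortest pressure interval stated anywhere is 15 minutes. Hypotension matters here: section 8.0.1 names it as a complication both of deep cooling in earlier case series and of higher pethidine doses.

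The dense schedules start at cooling, or run through cooling and warming, and controls have neither. If controls are in practice read less often, fewer of their episodes will be found, and cooling will look worse on this item for that reason alone. Among the cooled arms, the 5.6.2 window lengthens with depth and duration. Without a common window, longer exposure cannot be told apart from longer looking. Section 7.2 uses the safety comparison across depth and duration to choose the phase III strategy, and section 3 plans to pool these data with those of other centres.

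**Working it through.** **1. Window length.** Inputs: rewarming at no more than 0.3°C per hour to 36°C (5.6.2); cooling for 12 or 24 h. Minimum rewarming = (36 − target)/0.3:
- 35°C: 1/0.3 = 3.33 h
- 33°C: 3/0.3 = 10 h

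Both agree with the 3 h 20 min and 10 h stated in section 3 (Feasibility).

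**2. Scheduled readings over the same window** (cooling plus minimum rewarming, whole readings, time-zero reading excluded). For a window of W hours, 5.6.2 gives 4W and 6.0.3 gives 12 + 2(W − 3).

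| Arm | W (h) | 5.6.2 | 6.0.3 | Ratio |
|---|---|---|---|---|
| A, 35°C 12 h | 15.33 | 61 | 36 | 59% |
| B, 33°C 12 h | 22 | 88 | 50 | 57% |
| C, 35°C 24 h | 27.33 | 109 | 60 | 55% |
| D, 33°C 24 h | 34 | 136 | 74 | 54% |

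The half-hourly phase of 6.0.3 runs on to 12 h after the start of warming, so its full totals are 12 + 2(24 − 3) = 54 in the 12 h arms and 12 + 2(36 − 3) = 78 in the 24 h arms. Those totals cover different windows and should not be set against the 5.6.2 column.

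**3. Tympanic readings to 48 h after onset.** Assumption: cooling starts at the latest permitted time, 4.5 h, leaving 43.5 h.
- 2.2.2: 12 + 2 × 40.5 = 93.
- Section 3: 48 + 31.5, about 80 (12 h arms); 96 + 19.5, about 116 (24 h arms).
- 6.0.3: 54 + 3 = 57 (12 h arms); 78 + 1 = 79 (24 h arms).
- 5.6.2: no end stated, so no count is possible.

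**4. Can the hypotension criterion be observed?** For one episode of L minutes starting at random against readings every D minutes:
- P(at least one low reading) = min(1, L/D)
- P(at least two) = min(1, max(0, (L − D)/D))

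| L | D = 15: one / two | D = 30: one / two |
|---|---|---|
| 10 min | 67% / 0% | 33% / 0% |
| 20 min | 100% / 33% | 67% / 0% |
| 30 min | 100% / 100% | 100% / 0% |

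A single low reading says nothing about duration. Two low readings need an episode of at least 15 or 30 minutes. The 10-minute rule is therefore not decidable from either schedule.

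**5. Controls.** The protocol gives no early interval, so a range is needed. The chance that a 10-minute episode meets one reading is:
- 10/360 = 2.8% if only the 6-hourly phase applied (2 to 5 readings in the windows above)
- 10/60 = 17% if read hourly
- 33% or 67% if read as the cooled patients are

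The imbalance therefore runs from none to large.

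**The case against.** The strongest reply is that this is a descriptive pilot with arms of 4 and 8 controls, that its primary endpoint (completed interventions) is untouched, and that deriving an event from charted data is normally left to the analysis plan or the case record form. Much of that stands. It limits the seriousness, but it does not reconcile two conflicting instructions or supply data that neither schedule collects.

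Four stronger readings are tempting, and the protocol does not support them:

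- *The shivering endpoint cannot be obtained.* Section 3 provides for the Columbia score every 15 minutes. The fault is that the charting lists disagree with it; the score would be lost only if the record form followed those lists.
- *Oesophageal data are missing.* They are recorded continuously in cooled patients. The gap in 6.0.3 is one of consistency.
- *Controls are under-observed and the safety comparisons are biased.* The control interval is undefined, not stated to be lower. Section 6.0.3 is headed as running from randomisation, and all patients are in the same unit. ECGs are timed from randomisation, and NIHSS and adverse event recording are not tied to cooling. Deaths, haemorrhage needing transfusion, ICU admission and day-7 NIHSS do not rest on the vital-sign grid.
- *Arm D is always watched longest.* That holds under 5.6.2. For the half-hourly phase of 6.0.3, C and D share 36 h, and A and B share 24 h.

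**Conclusion.** The point holds in a limited form. Sections 5.6.2 and 6.0.3 contradict each other on blood pressure, consciousness and shivering, and 6.0.3 yields 54% to 59% of the readings in 5.6.2 over the same window. Tympanic intervals conflict across 2.2.2, 3, 5.6.2 and 6.0.3. The shivering lists do not match the stated endpoint. No stated pressure interval can establish the 10-minute hypotension criterion.

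Controls have no defined early interval, so hypotension, and any other event found mainly from frequent vital signs, is open to differential ascertainment. Its size is unknown and cannot be inferred from the protocol.

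The reading counts assume rewarming at the maximum permitted rate; slower rewarming lengthens the windows. The detection probabilities assume a randomly timed episode and evenly spaced readings. The point should be corrected before recruitment, but it does not threaten the primary endpoint.

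**What to change.** 1. Reconcile 2.2.2, 3, 5.6.2 and 6.0.3 to one observation schedule, timed from randomisation and identical in all arms, controls included. Which interval to adopt is for the investigators; the sections must agree.
2. State a common window from randomisation over which hypotension is compared between arms.
3. Keep the hypotension definition. In every arm, establish it by a repeat reading about 10 minutes after any reading below 70 mmHg, or from continuous monitoring in the High Dependency Unit where that exists. This is an ascertainment rule only, not a change in management.
4. Put the Columbia score in place of presence or absence of shivering in 5.6.2 and 6.0.3, and list oesophageal temperature in 6.0.3.

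Requiring two consecutive scheduled low readings would be a poor substitute for item 3: it catches 0% of 10-minute episodes and silently replaces the definition with a 15- or 30-minute one. The repeat reading confirms an episode when a scheduled reading falls at least 10 minutes before its end, so P = min(1, (L − 10)/D). For a 20-minute episode this is 10/15 = 67% or 10/30 = 33%, against 33% or 0% for two consecutive scheduled readings. It still misses episodes of barely 10 minutes; only continuous monitoring would catch those, and the limitation should be stated.

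The cost is protocol wording, record-form fields and more charting in 8 controls already in the High Dependency Unit. Using the table above, that is 36 to 136 readings per control depending on interval and window, or 8 × 36 = 288 to 8 × 136 = 1,088 in all, less whatever the unit already charts.
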